### **3. STUDY DESIGN**

#### **3.1 Type of Study**

This is an investigator-initiated multi-site, two-arm randomised controlled hybrid effectiveness-implementation trial of two e-PROM tools designed to help clinicians better manage patient care. The tools provide information only and thus are not classed as medical devices.

The traditional route to translation requires a study of clinical effectiveness and then a separate study to evaluate the implementation of the intervention in practice. This stepwise process is necessarily time-consuming and has led to the development of designs that allow both steps to be conducted in a single study [23]. We therefore propose a hybrid study that will test both effectiveness/cost-effectiveness and implementation.

#### **3.2 Study Sites and Study Population**

The study population will be adult (age  $\geq 18$  years) cancer patients about to start their first systemic anti-cancer therapy or radiation therapy at one of the trial sites. The trial will be run at PAH, RBWH, Townsville (TVH) and Gold Coast Hospitals (GCH) in Queensland. These sites were selected because PAH and RBWH are quaternary public health hospitals that provide integrated cancer care and, together, deliver outpatient care to ~3000 cancer patients each week. They have developed e-PROM tools (*My Health My Way* and *AboutMe*) and are well set up to evaluate these in a trial context. TVH and GCH are large regional hubs and have expressed an interest in using the e-PROM tools. Collectively, these public hospitals are well-placed to optimise and influence cancer care delivery in Queensland, and to inform a statewide approach to the use of e-PROMs.

#### **3.3 Number of Participants**

The study will recruit a minimum of 572 participants, 286 in each arm, across the four study sites. The recruitment target for each site is below but the exact numbers may vary:

PAH & RBWH	150-175
GCH & TVH	110-145

#### **3.4 Expected Duration of Study**

The active component of the study is expected to run for up to 3 years. It is anticipated that it will take 12 months to recruit participants and that the intervention and active follow-up will continue for up to 2 years. [Funding is currently available for 1.5 years follow-up but, if additional funding can be secured, we will continue active follow-up for an additional 6 months for a total of 2 years.]

##### **3.4.1 *Extended passive follow-up***

After the end of the active follow-up period, we will continue to monitor ongoing use of the e-PROM tools for an additional 12 months and will follow participants passively (through medical records and routine data linkage) for up to an additional 5 years. There will be no further contact with participants during this period. We will also conduct a brief survey with a sample of clinicians at each of the study sites at 6 and 12 months after study. This will ask whether the clinicians are still using the tools, how many and which patients they use them with (e.g. only former trial participants or also new patients), how often they use them and how they use the results.

## **4. PARTICIPANT ENROLMENT AND WITHDRAWAL**

### **4.1 Eligibility Criteria**

#### **4.1.1 Inclusion Criteria**

- Age at least 18 years;
- Diagnosed with an invasive solid cancer;
- About to start or recently started treatment at one of the study sites.

#### **4.1.2 Exclusion Criteria**

An individual who meets any of the following criteria will be excluded from participation:

- A tumour type or characteristic that is not appropriate for inclusion at the discretion of the Site Investigator and Coordinating PI e.g.:
  - Will not return to the site for regular treatment/follow-up;
  - Already using or would normally use an e-PROM tool at that site;
- Life expectancy less than 3 months
- Treated with surgery only;
- Current participation in another study that requires completion of similar PROMs;
- Unable to provide informed consent;
- Unable to complete the e-PROM tools remotely (e.g. a comorbid condition affecting vision, cognition or dexterity or no internet access at home)
- Unable to complete the study questionnaires in English;
- Unwilling to consent to data linkage.

In addition, participants who consent but do not complete the Baseline Study Questionnaire will be excluded post-consent.

### **4.2 Recruitment**

The Study Coordinator at each site will identify all patients attending participating clinics during the study period who meet the inclusion criteria. Patients who clearly meet one of the exclusion criteria will be flagged and the reason for exclusion recorded. The Study Coordinator will approach the remaining patients and briefly explain the study to them. If patients are interested in the study, the Study Coordinator will perform a final eligibility screen and record any additional reasons for exclusion. The Study Coordinator will conduct the informed consent discussion. They will give patients who pass all of the exclusion criteria the PROMISE Participant Information sheet and Consent Form (PICF) and will explain the study to them and answer any questions. The PICF will describe the purpose of the study, the procedures to be followed, and the risks and benefits of participation. The Study Coordinator will check that the participant understands the information provided. Patients will be advised that if they decline to participate, or initially consent but then choose to withdraw, this will not affect their future healthcare. All participants will also be asked to provide consent to obtain MBS and PBS data from Services Australia (PROMISE Medicare Consent Form).

Consent will be voluntary and free from coercion. When a patient consents to participate they will be given a copy of the consent form, they will be assigned a unique Study ID number and their consent will be recorded in the Study Database. When their consent is recorded, this will prompt the Database / Study RA (based at QIMR Berghofer) to send them a personalised link to complete the Baseline Study Questionnaire.

Basic information (age, gender, postcode, cancer type and stage, study site) will be recorded in the Study Coordinator's Log and the Study Database for patients who are excluded or who decline to participate, together with the reason for exclusion/non-participation. This is to allow participation rates to be calculated, both overall and within key demographic/clinical groups. The patient's name will also be recorded but this information will only be accessible to the Study Coordinator (to ensure the same participant is not approached twice) and it will be deleted at the end of the recruitment period.

#### **4.2.1 *PROMISE-Carers Substudy***

After they consent to participate in the main study, participants will be invited to nominate their partner/carer to participate in the Carer Sub-Study. They will be advised that this is optional and that they do not have to nominate a partner or carer. Nominated partners/carers will be approached, given a copy of the PROMISE Carer PICF and invited to participate.

#### **4.2.2 *PROMISE-Genetics Substudy***

Consenting participants will also be invited to participate in the Genetic Substudy. The Study Coordinator will describe the purpose of the Substudy and what it will involve. They will give the participant a copy of the PROMISE Genetic PICF and will answer any questions that the participant has. Participants will be advised that this aspect of the study is optional and if they choose not to participate this will not affect their participation in the main PROMISE trial. They will also be advised that they can withdraw from this aspect of the study at any time and that any blood samples already collected will be destroyed if they request this.

### **4.3 Treatment Assignment Procedures**

#### **4.3.1 *Randomisation Procedures***

Randomisation will be at the patient level, with a 1:1 ratio between groups, using randomly varied permuted blocks, stratified by sex, hospital, treatment intent (curative/palliative) and computer literacy (defined as regular access to a computer/tablet/smart phone and use of email  $\geq 1$ /week vs. less often) as this was shown to be important in previous trials [8, 9]. When a participant completes the Baseline Study Questionnaire, the central web-based database will automatically apply the next relevant record in the allocation sequence, as we have done previously [24-26].

#### **4.3.2 *Blinding Procedures***

All study staff/investigators will be blinded to the allocation sequence ensuring allocation concealment until study entry. Due to the nature of the intervention, participants, their treating clinicians and the Trial Coordinators at each site will not be blinded to group allocation; however, the other investigators and project staff, including those collecting outcome data and conducting analyses, will remain blinded until after the main analyses have been finalised and the first papers are being prepared for publication (see 10.3 Statistical Analysis).

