### 2.3.1 **Primary outcomes**

- (i) The rate of unplanned hospital presentations/admissions. This information will be obtained from hospital records and linkage to the Queensland Health Admitted Patients Data Collection (QHAPDC), Emergency Data and Medical Benefits Scheme (MBS) data.
- (ii) Physical and functional wellbeing measured by the Physical Wellbeing and Functional Wellbeing subscales of the Functional Assessment of Cancer Treatment – General (FACT-G) scale [15].

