### 2.3.2 **Secondary outcomes**

The secondary objectives will assess differences in a range of other key health-related outcomes that could be affected by the intervention.

- (i) Rates of treatment completion: proportion of planned treatment received; information about planned treatment, dose reductions and delays will be obtained from medical records.
- (ii) Overall wellbeing measured by the Functional Assessment of Cancer Treatment – General (FACT-G) scale [15].
- (iii) Levels of patient distress measured by the Hospital Anxiety and Depression Scale (HADS) using cut-points of  $\geq 10$  to indicate clinical anxiety or depression and 8-10 to indicate sub-clinical anxiety or depression [16, 17].
- (iv) Symptom burden measured by the Memorial Symptom Assessment Scale (MSAS) which assesses the presence, severity and distress caused by 32 individual symptoms [18].
- (iii) Numbers of out-patient visits; information will be obtained from hospital records and linkage to Emergency Data and Medical Benefits Scheme (MBS) data.

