#### 5.1.2 ***AboutMe***

*AboutMe* is managed at RBWH and operated via a Queensland Government QGov account to ensure data are stored and transmitted securely. When participants are randomised to the intervention group the site nurse will help them set up a QGov log-in and will show them how to use the *AboutMe* system. As for *My Health My Way*, the tool

can be accessed from anywhere by patients (via a unique link sent to them) and their approved healthcare providers.

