## 12.4 Data Capture Methods

Data capture methods will include:

- On-line questionnaires: Participants and participating partners/carers will be sent unique electronic links to allow them to complete the Study Questionnaires on-line. The data-entry interface will include in-built checks and prompts to maximise data quality and minimise missing data.
- Telephone interviews with participants and participating partners/carers: *these will only be required if the Study Questionnaires have not been completed on-line and/or the participant needs assistance.* A Research Assistant (blinded to the participant's group allocation) based at QIMR Berghofer will call relevant participants and either help them to complete the questionnaire or complete it with information by entering the information directly into the study database.
- In-person, telephone or videoconference interview with participants (patients, partners/carers and healthcare providers): to capture qualitative information about experience using the tools. These interviews will be recorded and transcribed at the end of the study by a professional transcriber.
- Clinical information from medical records: where possible, this will be entered directly into the study database via an interface that will include in-built checks and prompts to maximize data quality and minimise missing data. If direct entry is not possible, the information will be recorded onto a paper CRF by the site nurse and entered into the database as soon as possible after this. The paper record will then be shredded.
- Other health-related information will be obtained electronically via linkage to routine data collections and the e-PROM systems. An electronic list of study participants with key identifying information (e.g. name, date of birth, address, URN number) will be sent securely to the relevant data custodian who will return the resulting linked dataset according to their established protocols. Data transfer will be performed with assistance from QIMR Berghofer IT Department and following requirements of the various Data Custodians to ensure all electronic transfer of electronic data is secure.

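### Section 4.3.2 says outcome collectors are blinded, but medical-record data may be recorded by a site nurse who knows the arm, which leaves treatment completion exposed

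*Protocol*

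**What the plan says.** **Blinding claim.** Protocol 4.3.2 states that "participants, their treating clinicians and the Trial Coordinators at each site will not be blinded to group allocation". It then says that the remaining investigators and project staff, "including those collecting outcome data and conducting analyses, will remain blinded until after the main analyses have been finalised".

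**Who records medical-record data.** Under 12.4, "where possible, this will be entered directly into the study database via an interface"; no person is named for this route. Otherwise, "If direct entry is not possible, the information will be recorded onto a paper CRF by the site nurse".

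**What the site nurse does with the tool.** When a participant is randomised to the intervention at an *AboutMe* site, "the site nurse will help them set up a QGov log-in and will show them how to use" the system (5.1.2). At clinic visits the nurse checks the summary report and helps with completion (5.1). The nurse also records non-completion, the reasons for it and how much help was needed (5.3).

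**Outcome sources.** For treatment completion, "information about planned treatment, dose reductions and delays will be obtained from medical records" (2.3.2); Table 1 adds no linked source. Section 10.3.2 analyses the fraction of planned treatment received and the proportion above 85%. For the first primary outcome, 2.3.1 says "This information will be obtained from hospital records and linkage" to administrative collections, and Table 1 gives the same pair of sources.

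**The concern.** The protocol presents blinded outcome collection as a general property of the trial, with only the three named groups as exceptions. A role that must know the arm is also a named recorder of medical-record data.

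This matters most where recording calls for judgement and no independent source exists. Treatment completion fits that description. Someone must decide from the notes what was planned, and whether a later change was a reduction, a delay or a new plan. Section 7.1.3 collects clinical data at baseline and annually, but nothing requires the planned treatment to be entered before allocation. It could therefore be read from notes written after the arm was known. A small tendency to read the plan more generously in one arm would move patients across the 85% cut and appear as a treatment effect.

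**Working it through.** The protocol gives no figure on this point to reproduce. The check sets the sections side by side and then sizes the exposure under stated assumptions.

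**Step 1: can 4.3.2 and 12.4 both hold?** There are two cases.
- The site nurse is the Trial Coordinator. Section 4.2 gives the consent discussion to the Study Coordinator and section 11.2 gives it to the site nurse, so the roles may overlap. A role declared unblinded then collects outcome data.
- The site nurse is someone else. Section 4.3.2 then places the nurse among the blinded staff, which 5.1, 5.1.2 and 5.3 rule out.

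Either way, the statement about outcome collectors fails for data on the paper route. For direct entry the protocol names nobody, so blinding is not established there either.

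**Step 2: where is blinding actually arranged?** Sections 6.3, 7.1.2 and 12.4 say that the central staff who telephone for questionnaires are blinded. No similar statement exists for record abstraction. Section 2.3.4 expects hospital records to show clinical responses related to the e-PROMs, so the record itself can reveal the arm to any abstractor.

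**Step 3: treatment completion (illustration).** Inputs: 286 per arm (section 3.3) and 200 per arm (section 10.2). Assumed: 75% truly exceed the cut in both arms, and recording scores a further *b* of intervention patients as complete. With p0 = 0.75, p1 = 0.75 + b and p̄ their mean:

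- se0 = √(2p̄(1−p̄)/n)
- se1 = √((p0(1−p0) + p1(1−p1))/n)
- P(significant) = Φ((b − 1.96·se0)/se1) + Φ((−b − 1.96·se0)/se1)

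For b = 0.05 and n = 286: p̄ = 0.775, se0 = 0.0349, se1 = 0.0349. The first term is Φ((0.05 − 0.0684)/0.0349) = Φ(−0.53) ≈ 0.298 and the second is below 0.001, giving 29.9%.

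| Assumed bias b | 286 per arm | 200 per arm |
|---|---|---|
| 2 points | 8.7% | 7.5% |
| 3 points | 13.5% | 10.9% |
| 5 points | 29.9% | 22.3% |

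**Step 4: unplanned presentations (illustration).** Inputs from section 10.2: 1.09 events per person-year, 18 months, 242 per group. Assume no true effect, that a share *s* of events is known only from site records, and that a fraction *m* of those is missed in the intervention arm only. Then RR = 1 − s·m and SE(log RR) = √[(1/1.635 + 1/(1.635·RR))/242], where 1.635 = 1.09 × 1.5.

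| s | m | RR | Two-sided rejection rate |
|---|---|---|---|
| 0 | any | 1.00 | 5.0% |
| 10% | 10% | 0.99 | 5.2% |
| 20% | 20% | 0.96 | 8.8% |
| 100% | 10% | 0.90 | 30.3% |

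The effect is negligible when linkage supplies nearly all events, and large only if site records decide the count.

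**The case against.** **The sentence in 4.3.2 may be ambiguous rather than false.** It exempts site Trial Coordinators first, so the outcome collectors it calls blinded could be just the central questionnaire staff. Part of the personnel section is absent from the public text and might define site roles. This has some force, but it does not rescue the wording: a reader of 4.3.2 would conclude that medical-record outcomes are collected blind, and nothing in the protocol arranges that.

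**It would be too strong to say that the nurse abstracts all record-based outcomes.** The nurse is named only for the paper fallback. This objection stands.

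**A reader might infer that the first primary outcome is biased.** The documents do not support that. Section 7.1.3 does not list presentations or admissions among the clinical data. Section 7.1.4 obtains them by linkage, section 12.4 treats linkage as a separate electronic route, and section 10.2 describes the linked emergency data as close to complete. No section has the nurse judging whether an event was unplanned. What remains is that 2.3.1 and Table 1 also list hospital records and do not say which source prevails.

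**A reader might also argue that extra nurse contact brings more outside events into the intervention arm's record.** The protocol documents no such effect. It would count against the intervention, and linkage does not depend on events reaching the site record.

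**Baseline collection exists.** Section 7.1.3 and Appendix A include clinical data at baseline, so planned treatment may well be captured early. That reduces the exposure. It does not close it, because nothing says that this entry comes before allocation or is fixed afterwards.

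**Conclusion.** The inconsistency is real and limited. Blinded outcome collection, as 4.3.2 states it, does not hold for medical-record data on the paper route and is not established for direct entry. The outcome clearly exposed is treatment completion: it has one source, needs judgement about the plan, and is cut at a threshold. Under the assumptions in Step 3, the chance of a spurious significant result rises from 5% to between 8.7% and 29.9% with 286 per arm. The 75% completion rate and the 2 to 5 point biases are illustrative, come from no protocol figure, and apply to treatment completion only. They show sensitivity to a bias of that size, not that one will occur. For the first primary outcome the defect is an unstated order of precedence between sources, with little consequence if linkage decides.

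**What to change.** 1. **Correct 4.3.2.** State that medical-record outcomes may be collected by unblinded site staff, and limit the blinding claim to central questionnaire staff and analysts. Naming a different abstractor would not by itself make the present wording true, because the records can show the arm.
2. **Fix the denominator of treatment completion before allocation.** Enter planned treatment in the database at baseline and lock it before allocation is released. Section 4.3.1 triggers allocation automatically when the Baseline Questionnaire is completed, so the database must also require this entry. Afterwards, site staff enter only delivered treatment and dates. The fraction and the 85% flag are computed centrally on the dummy-coded dataset already foreseen in 10.3.
3. **Set precedence for the first primary outcome.** State in 2.3.1 and Table 1 that linked administrative data decide unplanned presentations and admissions, with hospital records only as a check.

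The cost is a wording amendment, a database lock rule and a programmed derivation. The downsides are a narrower blinding claim and one more data-entry step before randomisation.

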## 4.4 Participant Withdrawal

Participants may withdraw voluntarily from the study at any time upon request without this affecting their future treatment or care. Withdrawal may be complete (no further participation or follow-up) or partial (no further active participation but ongoing passive follow-up). If participants withdraw completely, their data will be deleted if they request this.

### 4.4.1 *Reasons for Withdrawal*

Participants may choose to withdraw from active participation in the study if:

- They no longer want the study investigators to access their medical records and/or revoke their consent for data linkage (complete withdrawal).
- They no longer wish to complete the study questionnaires (partial withdrawal).

An investigator may terminate a study participant's participation in the study if:

- It is identified that they meet an exclusion criterion (not previously recognised, or e.g. altered mental capacity) that would have made them ineligible to participate.
- A participant experiences a clinical adverse event (AE) or other medical condition or a situation occurs such that continued participation in the study would not be in their best interest.

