### 4.4.2 *Handling of Withdrawals/Discontinuation & Loss to Follow-up*

When participants consent to take part in the study they will be advised that they have the right to withdraw at any stage if they choose to do so and that this will not affect their future medical care. The PICF will also explain that, if they do withdraw, any data already collected will be retained and passive follow-up via their medical records and data linkage will continue unless they specifically request that the data be destroyed and/or passive follow-up cease.

If a participant chooses to withdraw from the study they will be invited to complete the final Study Questionnaire. The withdrawal and, where possible, the reasons for this will be recorded on the relevant page of the CRF by the Investigator or Site Coordinator. A participant will be withdrawn completely if they revoke their consent to allow access to their medical records/information or if they request information previously collected from them be deleted. All other withdrawals will be deemed 'passive'. Participants will not be asked to complete any other study questionnaires but ongoing passive collection of clinical data will inform analyses of key end-points that do not require patient-reported information.

Participants in the intervention group who withdraw will be able to continue to use the e-PROM system if they choose to do so. If participants in the intervention group decide they no longer want to use the e-PROM tool they will be encouraged to continue to complete the study questionnaires and/or to allow ongoing access to their medical records.

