## 5. **STUDY INTERVENTION**

### 5.1 **Intervention**

The full PROMISE intervention combines the e-PROM tools that participants will complete (5.1.1 and 5.1.2) and the associated implementation strategies (5.1.3). The e-PROM tools use validated instruments (DT and ESAS) that have been used in previous studies, are currently being used in the PROMPTCare system in New South Wales [27-29] and are recommended for use nationally by the Cancer Survivorship Group of the Clinical Oncology Society of Australia (COSA).

In addition to their usual care (Section 5.2), participants randomised to the intervention will be oriented to the use of the e-PROM tool (*My Health My Way* at PAH, TVH; *AboutMe* at RBWH, GCH) at their first treatment visit post-randomisation. A reminder service built into the e-PROM systems will prompt participants to complete the tool 48-72 hours before each subsequent clinic visit (for treatment or follow-up), as previous reports identify this as a feasible time frame for health services to action e-PROM data entered [30]. Participants will also be encouraged to complete the tool monthly between clinic visits to monitor their own progress and facilitate early detection of new problems or exacerbation of existing problems.

When participants arrive for their appointment, the site nurse will check the summary report, to ensure the tool has been completed and, if not, they will help the participant to complete it prior to seeing their clinician. Where feasible, they will give the participant a print-out of the report to take in when they see their clinician; the clinician will also be able to access the report electronically. The report will detail the most recent symptoms entered and their severity (severe, moderate, normal/mild according to standard cut-points) as well as trends over time. Hospital-specific protocols (co-designed with clinical staff – see Section 5.3) will also be used to generate a summary patient-risk profile (e.g. urgent, high, medium, low [30]) and provide recommendations for review/referral. Clinicians will then decide on and prioritise management according to individual patient need.

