### 10.3 **Statistical Analysis Plan**

Data analysis will be guided by a formal statistical analysis plan that will be finalised prior to any analyses being conducted. All analyses will be intention-to-treat but compliance with the intervention will be assessed and, if there is substantial non-compliance, per-protocol analyses will also be performed. In exploratory sub-group analyses, we will also conduct analyses stratified by e-PROM tool, study site, gender, computer literacy, cancer type and cancer stage (early vs. advanced).

To preserve the blinding during preliminary analyses, the Data Manager will generate datasets with participants' true allocation code replaced by a random dummy code. This will

be replaced by the true code when we perform the final analyses (as in the D-Health trial [26]).

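### Ending participation after randomisation for an exclusion criterion also appears to stop the study questionnaires, which could cause avoidable and possibly arm-related loss of 6-month FACT-G scores

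*Protocol*

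**What the plan says.** Randomisation happens when the baseline questionnaire is completed (Protocol 4.3.1), so terminations of trial participants can fall after allocation.

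- **Who may end participation, and why.** Section 4.4.1 states: "An investigator may terminate a study participant's participation in the study if". The first ground is "It is identified that they meet an exclusion criterion (not previously recognised, or e.g. altered mental capacity"; the sentence goes on to say that the criterion is one that would have made the person ineligible. The second ground covers an adverse event, another medical condition, or that "a situation occurs such that continued participation in the study would not be in their best interest".
- **What follows.** Section 4.4.2 defines complete withdrawal narrowly (consent to records revoked, or deletion of data requested) and treats all other withdrawals as passive. For these, "Participants will not be asked to complete any other study questionnaires", while clinical data are still collected. The offer of a final questionnaire is worded only for a participant who chooses to withdraw.
- **The relevant criterion.** Section 4.1.2 excludes anyone "Unable to complete the e-PROM tools remotely".
- **Who sees the problem.** In the intervention arm, "the site nurse will check the summary report, to ensure the tool has been completed" (5.1). Section 5.3 has nurses record non-completion, the reasons, and the help needed.
- **Blinding.** Section 4.3.2 says that "participants, their treating clinicians and the Trial Coordinators at each site will not be blinded to group allocation"; other investigators and project staff stay blinded.
- **Analysis.** Section 10.3 states: "All analyses will be intention-to-treat". Section 10.3.1 compares 6-month FACT-G physical and functional wellbeing by t-test, then by general linear models with baseline covariates.

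**The concern.** Eligibility should be settled at randomisation. Here a criterion can be applied afterwards, at an investigator's discretion, and the named example (altered mental capacity) is a state that often develops later. The consequence is more than stopping the intervention: the outcome questionnaires appear to stop as well.

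This affects one of the two primary outcomes. Physical and functional wellbeing at 6 months exists only if the participant is asked. The overall FACT-G, HADS, MSAS and EQ-5D scores come from the same questionnaires. An intention-to-treat principle, or a missing-data method in a later SAP, cannot bring back a score that was never requested.

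The loss may also be related to arm. Only the intervention arm is given the tool, and only there do nurses watch whether it is completed. If frail participants who cannot manage the tool were removed mainly from that arm, its mean FACT-G among those remaining would rise and the comparison would favour the intervention.

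**Working it through.** **Step 1: the route to a missing score.** A termination under 4.4.1 is a withdrawal by section heading. It is not complete in the sense of 4.4.2, so it falls into the passive group, for whom questionnaires stop. No other section describes how investigator terminations are handled. If this happens before 6 months, the FACT-G score for the primary comparison is not collected. Hospital presentations are still captured from records and linkage.

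**Step 2: the plan's own figures.** Section 10.2 gives 200 analysable per group, up to 30% drop-out, and 286 recruited per group.

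- 200 / (1 − 0.30) = 285.7, rounded up to 286, as stated.
- Power at 200 per group for 0.5 SD, two-sided 5%: 99.9%, consistent with the stated figure of more than 90%. (The protocol does not state sidedness; two-sided is assumed.)

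**Step 3: bias from unequal removal.** The protocol gives no termination rates by arm and no scores for those removed, so both are assumptions. Let p_I and p_C be the shares of participants, otherwise able to give a 6-month score, who are removed from the intervention and control arms. Let d be the amount in SD by which they score below those retained, taken as equal in both arms. Each observed arm mean is too high by p × d, so

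bias = (p_I − p_C) × d.

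With 200 per arm, the standard error of the difference is √(2/200) = 0.10 SD. Under no true effect,

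type I error = P(Z > 1.96 − bias/SE) + P(Z < −1.96 − bias/SE).

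| Removed, intervention vs control (assumed) | d (assumed) | Bias | Bias/SE | Type I error |
|---|---|---|---|---|
| 5% vs 1% | 0.5 SD | 0.02 SD | 0.2 | 5.5% |
| 5% vs 1% | 1 SD | 0.04 SD | 0.4 | 6.9% |
| 10% vs 2% | 0.5 SD | 0.04 SD | 0.4 | 6.9% |
| 10% vs 2% | 1 SD | 0.08 SD | 0.8 | 12.6% |
| equal in number and type | any | 0 | 0 | 5.0% |

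On 200 per arm, an excess of 4 to 8 percentage points is 8 to 16 participants. Against the 0.5 SD that section 10.3.1 calls clinically meaningful, 0.02 to 0.08 SD is 4% to 16%.

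**Step 4: a wider range.** With an excess of 1 to 10 percentage points, d from 0.25 to 1 SD, and the intervention arm reduced accordingly, the bias runs from 0.0025 to 0.10 SD and the type I error from 5.0% to 16.4%. The top of that range needs a 10-point excess, all of them a full SD worse.

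**The case against.** Several points against the concern have force.

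- **The decision-maker.** A reader might infer that unblinded site staff will make these decisions. Section 4.4.1 says only that an investigator may do so, and section 4.3.2 has both blinded and unblinded investigators. An unblinded decision is possible but not stated.
- **Detection in both arms.** A reader might infer that inability to use the tool can be seen only in the intervention arm. Capacity and internet access are screened before consent (6.1). Both arms must complete an online baseline questionnaire (6.2), and both receive online follow-up questionnaires with a blinded telephone call to non-responders (6.3). The same difficulties can therefore surface in controls. What remains is that the intervention arm has an additional layer of observation.
- **Response to non-completion.** The stated response is help and encouragement (5.1, 5.3), and those who no longer want the tool are encouraged to keep answering questionnaires (4.4.2). Nothing says that non-completion leads to termination. Being found ineligible and choosing to stop the tool are different situations, so their different handling is not in itself a contradiction.
- **Other routes.** Removing a control who later starts using a tool, or a patient whose prognosis worsens, goes beyond the text. The criterion on tool use describes status at entry.
- **Section 4.4.2 itself.** It is written mainly for participants who choose to withdraw. Its application to investigator terminations rests on the catch-all for other withdrawals.
- **Altered mental capacity.** In the protocol's own example, valid self-report may be impossible anyway.
- **Adjustment.** Baseline adjustment would remove any part of the deficit already present at baseline, so the figures above are towards the high side for an adjusted analysis.

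These points reduce the concern to a risk. They do not answer the core of it: the rule is open-ended in time, needs no blinded confirmation, and appears to stop questionnaires for people who could still answer.

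**Conclusion.** The point holds as a possible, avoidable source of missing data on the 6-month wellbeing outcome and the other patient-reported outcomes. The loss may differ by arm, because one exclusion criterion is more likely to be noticed where the tool is in use. The documents do not show that questionnaires will stop unequally or that the result will be biased, and they do not contradict intention-to-treat: no section removes terminated participants from the analysis. The hospital-presentation outcome is largely protected by continued passive follow-up.

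The size is unknown. Under the assumed 4 to 8 percentage-point excess and 0.5 to 1 SD deficit, the effect is small against 0.5 SD, though it can raise the type I error noticeably at the upper end; with balanced removals it disappears. This is an inexpensive improvement to a conduct rule, and it has to be made while data are being collected because uncollected scores cannot be recovered.

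**What to change.** Amend Protocol 4.4.1 and 4.4.2 to state that:

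1. a randomised participant found to meet an exclusion criterion is still asked for the study questionnaires (online or through the existing blinded telephone call) and kept in linkage for as long as able and willing, and is analysed as randomised;
2. any exclusion from the analysis after randomisation that is retained rests only on facts documented before randomisation and is confirmed by someone blind to arm;
3. terminations by an investigator are reported by arm, with reason and timing.

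Whether such a participant goes on using the e-PROM tool is a separate matter and need not be changed by this amendment.

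The cost is a wording amendment with ethics approval and a few more questionnaires through a process that already exists. The downside is that a few truly ineligible patients stay in the analysis.
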